7. To evaluate the effect of Secukinumab (300 mg, 4-weekly s.c.) combined with lifestyle intervention in comparison to Secukinumab alone on health-related quality of life, itch, pain and scaling as well as mental well-being	7. Absolute DLQI, relative change of DLQI, proportion of patients with DLQI 0/1, absolute WHO-5, relative change in WHO-5, absolute self-assessed itch, pain, scaling, relative change in self-assessed itch, pain, scaling in both treatment arms throughout the duration of the core study

Objectives	Endpoints
	
5. To explore the effect of Secukinumab (300 mg, 4-weekly s.c.) combined with lifestyle intervention in comparison to Secukinumab alone on biomarkers including but not limited to those linked to lipid, glucose, muscle and bone metabolism, liver fibrosis/steatosis, heart injury, as well as to inflammatory processes in a subgroup of 100 patients (50 treated with secukinumab and lifestyle intervention and 50 treated with secukinumab alone)	5. At baseline (week 0), week 16 and week 28 the following markers will be assessed: Free fatty acid serum profile, sThy-1, adiponectin, leptin, insulin, HOMA-IR, proinsulin, IL-6, TNF-alpha, M30 assay, IL-1 beta, IL-1Ra, IL-18, IL-18bp, P1NP, CTX, RANKL, OPG, sclerostin, NT-proBNP, CD154, and a 30-panel multiplex inflammatory cytokine and chemokines panel

2 Statistical methods

This section contains information that will be used to draft CSR Section 9.7 on statistical analysis.

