2.6 Analysis of secondary efficacy objective(s)

2.6.1 Analysis of secondary endpoints

PASI 75, 90 and 100 at weeks 1, 2, 3, 4, 8, 12, 16, 20, 24 and 28 will be analyzed analogous to the primary endpoint. Absolute PASI scores will be analyzed using a MMRM, with factors treatment, center, visit, visit*treatment interaction and covariate baseline PASI. The raw as well as the adjusted least squares means and their differences between treatment groups will be calculated for each visit together with their corresponding 95% confidence intervals and p-values.

The same MMRM model updated with relevant baseline covariate similar to primary endpoint will also be used for the analyses of the other continuous secondary endpoints hsCRP, HbA1c, fructosamine, fasting plasma glucose, LDL, HDL, total cholesterol, triglycerides, waist circumference, BMI, body weight, systolic and diastolic blood pressure, QoL-scores (Absolute DLQI total score, relative change from baseline of DLQI total score, absolute WHO-5 total score, relative change from baseline in WHO-5 total score, absolute self-assessed itch, pain, and scaling, relative change from baseline in self-assessed itch, pain, and scaling) and activity levels (steps per day).

All the patients reporting DLQI score = 0 or 1 will be considered as “Responders (0)”, whereas the patients reporting DLQI score ≥ 2 will be considered as “Non-responders (1)”.

Proportion of patients with DLQI score (0&1) i.e., DLQI responders will be evaluated in both the arms and will be compared using a logistic regression model with the factors treatment, center, visit, visit*treatment interaction and covariate baseline DLQI. The odds ratio and its 95% confidence interval (CI) and p-value will be reported. See [Appendix 5.3](#) for more details on PROs.

Note: For the subjects with fasting & non-fasting status, separate analyses will be performed for fasting plasma glucose, fructosamine, and HbA1c levels.

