2.6.2 Handling of missing values/censoring/discontinuations

Non-responder imputation will also be applied to all secondary response variables. For continuous secondary endpoints, all available measurements will be included in the Mixed Model for Repeated Measures (MMRM).

[REDACTED]

[REDACTED]

[REDACTED]

[REDACTED]

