5.2 Statistical models

5.2.1 Primary analysis

Logistic regression model

The proportions of patients who achieve a PASI 90 response at Week 28 for each treatment group will be compared using logistic regression analysis. The model will include treatment and center as fixed effect and with covariates PASI score at baseline (Visit 2).

The SAS procedure PROC GLIMMIX will be used with the following SAS code:

```
proc glimmix data=.... order=internal;  
class trtn1 cntr ;  
model response = trtn1 cntr basv2 / ddfm=kr error=binary  
link=logit;  
lsmeans trtn1 / cl diff oddsratio;  
run;
```

where

response = PASI 90 response (= 1 or 0)

trtn1 = treatment

cntr = center

basv2 = PASI score at baseline (Visit 2)

The estimated odds ratios will be displayed along with the associated 95% confidence intervals and p-values (two-sided).

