5.3 Patient reported outcomes (PRO)

PROs will be assessed by the following validated instruments.

- Dermatology Life Quality Index (DLQI®)
- Self-assessed pain, itching, scaling
- WHO-5

Dermatology Life Quality Index (DLQI®)

The DLQI® is a 10-item general dermatology disability index designed to assess Health-related quality of life (HRQoL) in adult subjects with skin diseases such as eczema, psoriasis, acne, and viral warts (Finlay and Khan, 1994; Basra et al., 2008).

The measure is self-administered and includes domains of daily activities, leisure, personal relationships, symptoms and feelings, treatment, and work/school. The measure is widely used: it has been tested across 33 different skin conditions and is available in 85 languages. The DLQI is the most frequently used instrument in studies of randomized controlled trials in dermatology. The recall period is the previous week, and the instrument takes 1 to 2 minutes to complete.

Each item has four response categories including 0 (not at all), 1 (a little), 2 (a lot), and 3 (very much). "Not relevant" is also a valid response and is scored as 0.

The DLQI[®] total score is the sum of the 10 questions. Scores range from 0 to 30, with higher scores indicating greater HRQoL impairment. Each subscale of the DLQI[®] may also be analyzed separately.

Meaning of DLQI Scores

- 0-1= no effect at all on subject's life
- 2-5= small effect on subject's life
- 6-10= moderate effect on subject's life
- 11-20= very large effect on subject's life
- 21-30= extremely large effect on subject's life

DLQI response 0/1 variable will be calculated based on the DLQI total score as follows:

- 0 – If DLQI total score is either 0 or 1
- 1 – If DLQI total score is > 1

DLQI percentage change from baseline will be calculated using DLQI total scores as follows:

$$((\text{post-baseline total DLQI} - \text{baseline total DLQI}) / (\text{baseline total DLQI})) * 100$$

Subject's self-assessed pain, itching and scaling

A self-administered, 11-point numeric rating scale (NRS, 0-10) will be used to evaluate the subject's assessment of their current pain, itching and scaling. Respondents will answer the following questions for the assessment of

- **Pain:** Overall, how severe was your psoriasis-related pain over the past 24 hours
- **Itching:** Overall, how severe was your psoriasis-related itch over the past 24 hours
- **Scaling:** Overall, how severe was your psoriasis-related scaling over the past 24 hours

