5.1 Statistical models

MMRM Model

Absolute biomarkers value will be analyzed using a Mixed Model for Repeated Measurements (MMRM) with factors treatment, center, visit, visit*treatment interaction and covariate baseline biomarker value.

```
proc mixed data = BAS covtest;  
class subjid TRT01P siteid avisitn;  
model CHG_B = base TRT01P siteid avisitn avisitn*TRT01P/ ddfm=KR  
residual;  
repeated avisitn / type=un subject=subjid rcorr;  
estimate "Trt diff at Week 28" Trt 1 -1 TRT01P*avisitn 1 -1/cl;  
lsmeans Trt*VisitWk / cl;  
run;
```

Where,

BAS = dataset; TRT01P = Treatment arms (A & B); CHG_B = Change from Baseline

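### SAP 2.6.1 pools seven visits of DLQI 0/1 in one logistic model without specifying within-patient correlation or which odds ratio is reported; a visit-averaged p-value would be too small

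*SAP*

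**What the plan says.** SAP 1.2 defines the DLQI 0/1 proportion as one of several items under the seventh secondary objective, to be evaluated "in both treatment arms throughout the duration of the core study". SAP 2.6.1 gives the method: the arms are "compared using a logistic regression model with the factors treatment, center, visit, visit*treatment interaction and covariate baseline DLQI". On the output it says only: "The odds ratio and its 95% confidence interval (CI) and p-value will be reported". It does not name a visit for that odds ratio.

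Other places that bear on the point:

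- Protocol Table 6-1 schedules DLQI at visits 6 to 12, that is Weeks 4, 8, 12, 16, 20, 24 and 28: seven post-baseline assessments in the core study.
- SAP 2.6.2: "Non-responder imputation will also be applied to all secondary response variables". Every patient therefore has a row at every visit.
- SAP 5.3, to which 2.6.1 refers for details, covers scoring only. It assigns the value 0 as follows: "If DLQI total score is either 0 or 1". SAP 2.6.1 likewise labels responders 0 and non-responders 1. The primary code uses "response = PASI 90 response (= 1 or 0".
- The only logistic code is in SAP 5.2.1, for one visit: "model response = trtn1 cntr basv2 / ddfm=kr error=binary". It has no RANDOM statement, and its odds ratio comes from an `lsmeans trtn1` statement.
- The biomarker sub-study SAP, section 5.1, does name the patient in its repeated-measures code: "repeated avisitn / type=un subject=subjid rcorr".
- Protocol 9.5.1 places the DLQI 0/1 proportion in the list of continuous endpoints for the MMRM. SAP section 4 does not list the switch to logistic regression among the changes.

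**The concern.** A patient with DLQI 0 or 1 at one visit is likely to have it at the next. A logistic model that stacks seven visits and treats the rows as independent counts much of the same information more than once. The estimate of a visit-averaged treatment effect is not the problem; its standard error is. The confidence interval would be too narrow and the p-value too small.

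Whether this happens depends on two things the SAP leaves open: whether within-patient correlation is modelled, and which contrast is reported. The nearest template points the wrong way on both. With visit and its interaction with treatment added to the SAP 5.2.1 code, `lsmeans trtn1` averages the treatment contrast over the seven visits, and nothing in that code links a patient's rows. DLQI is self-reported in an open-label trial, so a spuriously small p-value would be easy to over-read.

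**Working it through.** **Plan's own figure.** The documents give no power, variance or correlation for DLQI 0/1, so there is nothing to reproduce for this endpoint. (The 342 per arm for PASI90 does reproduce with a continuity-corrected two-proportion formula, but it does not bear on this point.)

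**Inputs from the documents.** Seven visits (protocol Table 6-1); 380 per arm, 1:1 (SAP section 3, protocol 5.3); about 100 sites (protocol section 4); two-sided 5% level (SAP 2.1.1). Rows in the model: 760 × 7 = 5,320.

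**Assumption.** The within-patient correlation ρ of the binary response, shown over a range.

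**Step 1, analytic, visit-averaged contrast.** With m = 7, the variance is understated by DE = 1 + (m − 1)ρ = 1 + 6ρ. The false-positive rate of the naive test is 2 × [1 − Φ(1.96/√DE)]. A correct two-sided p of 0.20 (z = 1.2816) would be printed as 2 × [1 − Φ(1.2816 × √DE)].

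| ρ | DE | √DE | False positives at nominal 5% | Correct p = 0.20 prints as |
|---|---|---|---|---|
| 0.2 | 2.2 | 1.48 | 19% | 0.057 |
| 0.3 | 2.8 | 1.67 | 24% | 0.032 |
| 0.5 | 4.0 | 2.00 | 33% | 0.010 |
| 0.7 | 5.2 | 2.28 | 39% | 0.003 |

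**Step 2, simulation with no treatment effect.** 380 per arm, seven visits, the SAP's fixed effects, a logistic random intercept per patient to create the correlation, and 500 runs per setting. Naive standard errors are compared with patient-clustered (sandwich) ones. Monte Carlo error (95%) is about ±2 points near 5% and ±4 points near 30%.

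| Centers | Mean ρ | Averaged, naive | Averaged, clustered | SE ratio, averaged | Week 28, naive | Week 28, clustered | SE ratio, Week 28 |
|---|---|---|---|---|---|---|---|
| 100 | 0.18 | 19.4% | 8.0% | 1.33 | 5.2% | 5.2% | 1.01 |
| 100 | 0.37 | 31.0% | 7.0% | 1.71 | 7.4% | 6.4% | 1.02 |
| 100 | 0.53 | 36.2% | 7.6% | 1.99 | 6.4% | 5.6% | 1.03 |
| 20 | 0.37 | 30.0% | 5.0% | 1.76 | 5.4% | 5.2% | 1.00 |

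The SE ratio is clustered over naive.

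**Step 3, reading the results.** The simulated error rates for the averaged contrast agree with Step 1. The Week 28 contrast is almost untouched: because the model contains the visit-by-treatment interaction, that contrast rests almost entirely on the Week 28 rows, one per patient. Averaged over all seven visit-specific naive tests, the rejection rates with 100 centers were 5.6%, 6.8% and 7.2%; with 20 centers the rate was 4.9%. The small excess with 100 centers, including the 7% to 8% left after clustering, is consistent with fitting about 100 center effects, since it disappears with 20.

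**The case against.** The strongest reply is that the SAP is under-specified rather than shown to be wrong.

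- **The contrast is not stated.** A reader might infer that the DLQI p-value will necessarily be far too small. The documents do not support that. The wording about the odds ratio is nearly the same as for the single-visit primary endpoint, and the MMRM results in the same section are promised for each visit, so a per-visit or Week 28 odds ratio is a fair reading. For that reading the distortion is negligible (SE ratio 1.00 to 1.03).
- **No patient term is inferred from silence.** The SAP's prose for the MMRM also omits the subject; in the biomarker SAP it appears only in code. There is no DLQI code, and GLIMMIX can model within-patient correlation. This stands in part: it is right to say that none is specified, not that none will be used. But MMRM implies repeated measures by its name, and logistic regression does not.
- **Size.** A reader might think each patient's information is counted seven times over. That would need a correlation of 1; over the assumed range the factor is 2.2 to 5.2.
- **Importance.** DLQI 0/1 might be taken as the main quality-of-life endpoint. SAP 1.2 does not rank it, absolute and relative DLQI change are analysed separately by MMRM, and no success claim depends on it.
- **Coding.** Responder = 0 is openly labelled in SAP 2.6.1 and 5.3. Odds ratios would run in opposite directions for DLQI and PASI only if the primary code were reused unchanged, which no section says. This is a labelling matter.

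What survives is that the SAP allows, and its only logistic template leads to, the affected contrast without any adjustment.

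**Conclusion.** The point holds conditionally. SAP 2.6.1 pools seven visits, specifies no within-patient correlation and does not say which odds ratio it reports. If the primary code is extended literally, the reported odds ratio is a visit average with an understated standard error: about 19% to 39% false positives at a nominal 5% for assumed correlations of 0.2 to 0.7. The exact size rests on that assumption. Non-responder imputation turns dropouts into runs of non-response, which would add to the correlation. If a Week 28 or other visit-specific odds ratio is reported, the result is close to correct even from the naive model. The endpoint is secondary, and the primary PASI90 test is unaffected. Separately, the move from the protocol's MMRM to logistic regression is sensible for a binary endpoint but undocumented.

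**What to change.** In SAP 2.6.1:

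1. State that the Week 28 odds ratio is reported first, with the other visits as supporting results.
2. Preferred: fit a separate logistic model at each visit, with treatment, center and baseline DLQI, as is already done for PASI 75/90/100. Each patient then contributes one row per model and the correlation question disappears. These separate fits were not simulated here; they carry the same roughly 100 center terms as the primary model.
3. Alternative: keep one model but fit it by GEE, or in GLIMMIX with patient as subject, using robust variance, and request visit-specific contrasts. If a visit-averaged effect is also shown, note that with about 100 fixed center effects its test may stay slightly liberal (7% to 8% in the simulation).
4. State that the modelled event is response (DLQI 0/1), so that an odds ratio above 1 favours the same arm as for PASI.

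In SAP section 4, list the change from the MMRM of protocol 9.5.1 to logistic regression for this endpoint.

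The cost is a few sentences and a few lines of code. No data collection, sample size or primary analysis changes.

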2.6.2 Handling of missing values/censoring/discontinuations

Non-responder imputation will also be applied to all secondary response variables. For continuous secondary endpoints, all available measurements will be included in the Mixed Model for Repeated Measures (MMRM).

[REDACTED]

[REDACTED]

[REDACTED]

[REDACTED]

2.7.5 Effect of Secukinumab combined with lifestyle intervention on a biomarker sub-study

A biomarker sub-study will be performed during the core study to explore the effect of Secukinumab (300 mg, 4-weekly s.c.) combined with lifestyle intervention in comparison to Secukinumab alone on biomarkers in a subgroup of 100 patients (50 treated with secukinumab and lifestyle intervention and 50 treated with Secukinumab alone).

At baseline (week 0), week 16 and week 28 the following markers will be assessed using fasting blood samples: Free fatty acid serum profile, sThy-1, adiponectin, leptin, insulin, HOMA-IR, proinsulin, IL-6, TNF-alpha, M30 assay, IL-1 beta, IL-1Ra, IL-18, IL-18bp, P1NP, CTX, RANKL, OPG, sclerostin, NT-proBNP, CD154, and a 30-panel multiplex inflammatory cytokine and chemokines panel. All endpoints of the biomarker sub-study will be summarized by visit and analyzed using the same MMRM model as described in [section 2.6.1](#).

Only patients participating in the biomarker sub-study will be considered for this analysis. As the biomarker sub-study is planned to be conducted for the biomarkers samples collected under fasting conditions, so the subjects with non-fasting status will be analysed separately and independently.

2.8 Additional analysis

In order to explore the additional effect of lifestyle intervention on various related end-points an additional analysis will be performed for PASI 75, PASI 90 & PASI 100 and all the study biomarkers at V9 (Week 16), V12 (Week 28) and end-of-study i.e. Week 56 for both treatment arms, separately based on three below mentioned subgroups:

- Patients with weight loss <5%
- Patients with weight loss $\geq 5\%$ - < 10%
- Patients with weight loss $\geq 10\%$

For all the above mentioned sub-groups no. of patients falling in each sub-group will be descriptively summarized using frequency, percentages and exact 95% clopper-pearson CI at V9 (Week 16), V12 (Week 28) and end-of-study i.e. Week 56 for both treatment arms, separately using FAS. Change in weight loss will be compared from the baseline weight.

All the patients who achieved PASI 75, 90 & 100 at V9 (Week 16), V12 (Week 28) and end-of-study i.e. Week 56 will be descriptively summarized using frequency, percentages and exact 95% CI using clopper-pearson method for the above mentioned sub-groups in both treatment arms, separately using FAS. Further additional analysis will be performed on FAS dataset comparing treatments with respect to the PASI 75, 90 & 100 in a logistic regression model with the factors treatment, center and covariate baseline PASI. The odds ratio and its 95% confidence interval (CI) and p-value will be given. The above analysis will be performed for all the three sub-groups independently.

PASI score at baseline & PASI 75, 90 & 100 scores and biomarkers value will be descriptively summarized using N, n, Mean, median, standard deviation, min, max for all the three subgroups using FAS. All the summary statistics and analysis on biomarkers will be performed

only for the patients participating in Biomarker substudy. Further, PASI 75, 90 and 100 scores at V9 (Week 16), V12 (Week 28) and end-of-study i.e. Week 56 will be analyzed for all the three sub-groups, separately. Absolute PASI scores will be analyzed using a Mixed Model for Repeated Measurements (MMRM) with factors treatment, center, visit, visit*treatment interaction and covariate baseline PASI. The raw- as well as the adjusted (LS-) means and their differences between treatment groups will be calculated for each visit together with their corresponding 95% confidence intervals and p-values, for all the three sub-groups separately. Also, similar MMRM model will be used for the biomarkers Free fatty acid serum profile, sThy-1, adiponectin, leptin, insulin, HOMA-IR, proinsulin, IL-6, TNF-alpha, M30 assay, IL-1 beta, IL-1Ra, IL-18, IL-18bp, P1NP, CTX, RANKL, OPG, sclerostin, NT-proBNP, CD154, and a 30-panel multiplex inflammatory cytokine and chemokines panel for all the three sub-groups, separately.

All the above mentioned analysis for PASI 75, 90, 100 & all study biomarkers will be performed separately for both treatment groups for below mentioned comparisons:

- a. Patients with weight loss $\geq 5\%$ - $< 10\%$ vs. Patients with weight loss $< 5\%$
- b. Patients with weight loss $\geq 10\%$ vs. Patients with weight loss $< 5\%$

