Extension period: After 28 weeks the study continues with an extension period, during which lifestyle intervention is offered to all patients, irrespective of their prior treatment arm. This means that patients of arm B, who are willing to, can continue their previously started lifestyle intervention program and patients of arm A, who are willing to, can start the lifestyle intervention program at the beginning of the extension period. **All patients, irrespective of their decision whether to start/ continue lifestyle intervention or not, have to participate in the extension period and visit their dermatologic study center for scheduled visits.** The extension period ends at week 56, where all patients complete the study. There will be no study drug supply during the extension period. The treating physician can choose psoriasis therapy freely according to his discretion.

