3.2 Rationale for study design

This study design was chosen in order to be able to demonstrate that the combination of Secukinumab (300 mg, 4-weekly s.c.) with lifestyle intervention results in higher psoriasis treatment efficacy compared to Secukinumab alone in psoriasis patients with concomitant metabolic syndrome. Therefore a randomized study set up with two treatment arms was chosen, arm B, where patients receive Secukinumab treatment combined with lifestyle intervention and arm A as active comparator control group, where patients receive Secukinumab alone.

The design enables assessment of the additional effects of concomitant lifestyle intervention on psoriasis treatment efficacy of Secukinumab as well as on metabolic status of the patients.

The open-label design is a consequence of the lifestyle intervention, which would be very difficult to blind. This might theoretically lead to a certain bias concerning psoriasis severity assessments (PASI), as investigators could expect patients receiving additional lifestyle intervention to show stronger improvements. On the other hand lifestyle intervention is no drug therapy and is not established as therapeutic intervention in psoriasis therapy, which limits the bias. Furthermore the study includes an extension period, which offers lifestyle intervention to

all patients and which includes a final PASI assessment at the end of the extension period, thereby further limiting the bias. Other, secondary objectives, like improvement of glucose and lipid metabolism, reduction of blood pressure, weight loss or changes in biomarker levels are based on laboratory parameters (HbA1c, lipid panel, biomarkers) or technical measurements (blood pressure, body weight), where the influence of a potential bias is highly limited.

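### SAP 2.8 appears to extend its between-arm models of the added effect of lifestyle to Week 56, when the secukinumab-alone control is no longer maintained by design

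*SAP*

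**What the plan says.** SAP 2.8 states its aim: "In order to explore the additional effect of lifestyle intervention on various related end-points an additional analysis will be performed". The same sentence covers PASI 75, 90 and 100 and goes on to "all the study biomarkers at V9 (Week 16), V12 (Week 28) and end-of-study i.e. Week 56 for both treatment arms, separately", by three bands of weight loss from baseline (below 5%, 5% to below 10%, 10% or more).

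The section then sets out between-arm models:

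- For PASI response it plans an analysis "comparing treatments with respect to the PASI 75, 90 & 100 in a logistic regression model", adjusted for center and baseline PASI, with odds ratio, 95% CI and p-value, in each band independently.
- It names the visits again: "PASI 75, 90 and 100 scores at V9 (Week 16), V12 (Week 28) and end-of-study i.e. Week 56 will be analyzed", once more by band.
- For absolute PASI it plans an MMRM with treatment, visit and their interaction. Adjusted means are reported and "their differences between treatment groups will be calculated for each visit together with their corresponding 95% confidence intervals and p-values", by band.

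On the period after Week 28, protocol 3.1 says that "patients of arm A, who are willing to, can start the lifestyle intervention program at the beginning of the extension period", and that "There will be no study drug supply during the extension period". The physician chooses psoriasis therapy, and Table 5-1 places no restriction on treatment in the extension. Lifestyle participation is optional there for both arms.

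**The concern.** Protocol 3.4 chooses secukinumab without lifestyle as the comparator so that the added effect of lifestyle can be isolated. That separation is protected only during the core study, when arm A was kept out of the programme (protocol 3.2, fourth reason for the extension). SAP 2.8 uses the same treatment factor, under the same stated aim, at a visit where neither the lifestyle contrast nor the common drug background is still controlled.

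The stake is interpretation. A Week 56 odds ratio near 1 would look like a fading lifestyle benefit when the control arm may have received the programme. A raised odds ratio would look like a lasting benefit when the arms may simply have moved to different drugs.

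**Working it through.** The plan gives no figure for a Week 56 comparison. Its only sized comparison is PASI90 at Week 28, so there is nothing to reproduce for this point. The check sets the passages side by side.

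**Step 1. Does the between-arm inference reach Week 56?** The logistic-regression sentence names no visit, and the MMRM sentence refers to every visit without listing them. Week 56 comes from the opening sentence of 2.8 and from the later sentence that names it again for the PASI responses. Together these make Week 56 the natural reading, but it is a reading and not an explicit instruction.

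**Step 2. What separates the arms at each time?**

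| | To Week 28 | Week 28 to Week 56 | Source |
|---|---|---|---|
| Arm A lifestyle | Not allowed | May start; first visit Week 28 | Protocol 3.1, 3.2; SAP 2.4.2.2 |
| Arm B lifestyle | Mandatory | Optional; may stop | Protocol 3.1, 5.5.3.2 |
| Study drug | Secukinumab 300 mg, last injection Week 24 | None supplied | Protocol 3.1 |
| Psoriasis therapy | Restricted while on study drug | Any, physician's choice | Protocol Table 5-1, 3.1 |

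At Week 56 an arm A patient may have had 56 − 28 = 28 weeks of lifestyle. Every patient is 56 − 24 = 32 weeks past the last scheduled study injection.

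**Step 3. What does the contrast then estimate?** Take the whole randomised arms. Let δ be the lifestyle effect, u the share of arm A that starts, v the share of arm B that stops, and D the difference due to drug choice. Assume for simplicity that starters gain all of δ and stoppers lose all of it. Then

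Week 56 difference = δ(1 − u − v) + D.

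This equals δ only if u = v = 0 and D = 0. It is D alone when u + v = 1, and the lifestyle term changes sign when u + v exceeds 1. The documents give no value for u, v or D, so the formula shows how the result could mislead, not by how much.

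**Step 4. Is this handled elsewhere?** Neither SAP 2.8 nor the list of changes in SAP section 4 says how lifestyle uptake in arm A, stopping in arm B or a change of psoriasis drug is treated at Week 56. The biomarker SAP, section 2.6, repeats this additional analysis at Weeks 16 and 28 only. The extension SAP, section 5.2, gives statistical models as not applicable. The live question is therefore the Week 56 PASI.

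**Step 5. How many results are affected?** There are 3 PASI responses × 3 bands = 9 odds ratios, and 1 absolute PASI difference × 3 bands = 3. That makes up to 9 + 3 = 12 between-arm PASI contrasts at Week 56.

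**The case against.** The strongest reply is that the analysis is labelled additional and exploratory, that no claim rests on it, and that its model sentences do not themselves name Week 56. Parts of the plan are also not visible: several subsections of SAP 2.7, protocol 9.6, and section 2.5 of the extension SAP, whose contents list includes a model and method of analysis. A suitable analysis by extension participation could sit there. All of this stands, and it limits the severity. It does not remove the mismatch between the aim stated in 2.8 and what a Week 56 arm contrast can show. The contrasts between weight-loss bands within each arm, which close the section, do not use arm A as a control and are outside this point.

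Three stronger readings are tempting and are not supported:

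- **That the control has ceased to exist.** Lifestyle is optional, and protocol 7.2.2 foresees marketed secukinumab in the extension. Some arm A patients may therefore still be on secukinumab without lifestyle. They are self-selected, so the comparison is no longer maintained by design, but it has not vanished.
- **That a loss of power can be quantified.** A reader might apply assumed uptake to the design figures (81% against 90%, 342 per arm). Those figures are for whole arms at Week 28. The visible Week 56 models run inside weight-loss bands, no Week 56 response rate is assumed, and uptake is not documented.
- **That protocol 3.2 must be corrected as part of this.** It says that the extension "includes a final PASI assessment at the end of the extension period, thereby further limiting the bias". One may doubt this, since assessment stays open label. But the rationale also leans on lifestyle being offered to everyone, so the comparator argument alone does not rebut it, and deleting the sentence would change no analysis.

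**Conclusion.** The point holds as a minor one. As planned, a Week 56 between-arm result from SAP 2.8 would be reported as exploring the added effect of lifestyle. At best it reflects an early against a delayed offer of lifestyle under free-choice therapy. Inside the weight-loss bands even that is weakened, because the bands are defined by weight change after randomisation.

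The conclusion rests on two things: reading Week 56 into the models from the section as a whole, and the visible text alone. It does not depend on any particular uptake, because what changes at Week 28 is the design. The size of any distortion cannot be given from the documents. The reach is up to 12 exploratory PASI contrasts. The primary analysis and the Week 16 and 28 time points are not affected by this issue.

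**What to change.** In SAP 2.8:

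1. Restrict treatment-factor models, odds ratios, mean differences and p-values to Weeks 16 and 28, in line with section 2.6 of the biomarker SAP.
2. At Week 56, report PASI 75, 90 and 100 and absolute PASI descriptively by randomised arm. Show lifestyle participation (started or not in arm A, continued or stopped in arm B) and the psoriasis therapy used in the extension. State that these groups are self-selected and do not support causal comparison.
3. If a Week 56 arm contrast is kept, make it on the randomised arms without weight-loss bands, and label it as early versus delayed offer of lifestyle under free-choice therapy.

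The cost is SAP wording and table shells. Lifestyle attendance and concomitant therapy are already recorded in the extension. The downside is that option 2 gives no inferential Week 56 result, which agrees with the visible extension SAP.
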